### **General Magnetic Resonance Imaging Procedure**

The study subjects will be scanned with a 3.0 Tesla Philips Ingenia CX whole body clinical MRI system located at the Wright Center of Innovation of The Ohio State University Medical Center. The built-in body volume coil will be used for radio frequency (RF) transmission, and a phased array coil will be used to pick up the MRI signal. Anatomical and angiographic MR images will be acquired for one of the most commonly used flap surgery donor perforators including but not limited to:

- The deep inferior epigastric perforators (DIEP);
- The superior gluteal artery perforators (SGAP);
- The inferior gluteal artery perforators (IGAP);
- The thoracodorsal artery perforators (TDAP);

- The anterolateral thigh (ALT) perforators.

Upon the investigator's decision, all or part of the following imaging sequences will be acquired:

- Fast, low-resolution localizer.
- Reference scan for phased-array coil signal intensity inhomogeneity correction with the CLEAR technique.
- B1 calibration sequence for the RF field inhomogeneity correction with the Multi-Transmit technique.
- Typical anatomical imaging sequences (e.g., T2-weighted).
- Phase-contrast angiography.
- Susceptibility-weighted venography.
- Subcutaneous vascular imaging sequences using intrinsic contrast (e.g. T1 contrast and chemical shift contrasts).

The angiographic sequences may be repeated multiple times with different combinations of scanning parameters and acquisition hardware for the purpose of protocol optimization (for details see below). The scan time for each visit will be no greater than 60 minutes for the subject's comfort. If all planned sequences cannot be acquired within the first visit, an investigator or study key personnel will contact the subject after the scan and arrange additional visits upon the subject's willingness for continuous participation.

In MRI examinations,

- Volunteers may experience a metallic taste while entering or leaving the MRI system.
- Metallic objects can be accelerated by the magnetic field and become projectiles. Volunteers will be evaluated prior to entering the MRI system to exclude metal objects. Metal objects are excluded from the MR suite.
- If volunteers have a metal implant or foreign object in your body, the object could be displaced by the magnetic field. There can be increased heating near metal structures. If volunteers have any implants in their body, they will inform the researcher conducting this study, and they will not be eligible to participate in this study.
- Volunteers will be placed in the long tube of the MRI system. Some volunteers may have a claustrophobic reaction (uneasiness at being in a confined space). If this happens, volunteers will be asked if they wish to continue, or if they would like to terminate the study.
- Volunteers will hear loud thumping sounds that may be annoying. Volunteers will be supplied with earplugs that you should wear while they are in the MRI system.
- Exposure to the rapidly changing electrical fields could cause twitching of your muscles. This effect is usually temporary.

- When volunteers close their eyes, they might see tiny light flashes similar to those that occur when they rub their eyes in the dark. This has no known harmful effects.
- All these listed effects are transient, that is, seeing light flashes, metallic taste and muscle twitching will end once exposure to the MRI fields is ended. Based on this, effects of repeated MRI studies are not expected, however, long-term effects are not known at this time.

### **Imaging Protocol Optimization**

Development and optimization of perforator imaging protocols will be conducted with phantoms and volunteers.

The quality of MR images is determined by a large number of hardware, acquisition, and postprocessing factors. According to our previous experience, we identified the following factors as the most critical for this study:

1. Spatial resolution: While a higher spatial resolution is generally required to detect smaller objects (such as small blood vessel branches) in an image, the SNR of MR image is also proportional to the voxel volume. When the spatial resolution is decreased to some threshold level, stochastic noise will dominate in the image and mask important anatomical structures of interest.
2. Physiologic gating: Respiratory and cardiac motions can generate ghosting artifact and image blurring in MR images, especially in thoracic and abdominal regions. Because perforators are small vessels (whose diameters are typically between 500  $\mu\text{m}$  to over 1 mm), the influence of physiologic motion needs to be carefully controlled to allow effective visualization of perforators.
3. Parallel imaging: The use of parallel imaging techniques, such as Sensitivity Encoding (SENSE), can substantially reduce image acquisition time, thus minimizing image blurring and ghosting artifacts caused by subject motion. However, it also decreases the image SNR, and may cause reconstruction artifacts if the SENSE factor is set outside the optimal range.
4. Maximum phase-contrast velocity: In phase-contrast angiography, the maximum phase-contrast velocity specifies the maximum blood flow velocity that can be accurately encoded as brightness in the MR image. If this parameter is set too low, higher blood flow velocities will be phase-wrapped and the corresponding vessels may be invisible in the angiography image; if this parameter is set too high, the image contrast will be compressed. The vessel-of-interest may not have enough signal to be recognized from background noise.

Therefore, we plan to optimize our imaging protocols by testing various combinations of the four parameters mentioned above.

Other acquisition parameters, such as the repetition time (TR), echo time (TE), and flip angle (FA), will be determined by the investigator for each individual sequences based on our previous experience with those sequences and computer simulation of magnetization evolution at 3.0 Tesla.

The MR images will be reviewed by the research team after acquisition. The investigator will grade the overall image quality on a semi-quantitative scale. The protocol with the highest image quality score will be identified as the optimal protocol, which will be used in the clinical patient group.

### **Clinical CTA Data Extraction**

For patient subjects who had at least one pre-operative CTA performed at OSUMC within the past 48 months, or will have at least one pre-operative CTA performed at OSUMC prior to a scheduled flap procedure, an investigator will review their CTA cases available on OSUMC PACS and select the most recent one for further comparison and evaluation.

For patient subjects who do not have any pre-operative CTA on OSUMC PACS and are not expected to get one within the next 24 months, a radiologist will review previously acquired CTA cases saved on OSUMC PACS that were obtained in the past 48 months, and select an age- and gender-matched case with clear depiction of the relevant perforator(s) for further comparison and evaluation.

Comparison with clinical CTA is not necessary for volunteer data acquired for protocol development and optimization purposes.

The selected CTA data set will be retrieved from the Ohio State University Wexner Medical Center Picture Archiving and Communication System (OSUWMC PACS) and downloaded to a research data server protected by secure password and firewall. The downloaded data will be immediately de-identified with validated software and verified by imaging Corelab staff.

On investigational images, any incidental findings will be shared with the participant and his/her primary care physician who was identified during the consent process. However, the investigational images are not diagnostic and do not replace usual care.

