## OBJECTIVE

The perforator flap is a new improvement in reconstructive microsurgery that is increasingly gaining popularity in many different reconstructive applications to breast, torso, and extremities [Saint-Cyr 2009; Geddes 2003]. Because there is considerable inter-patient variation in the number, size, and position of perforator vessels, success of perforator flap surgery relies on state-of-the-art preoperative planning based on detailed understanding of the three-dimensional (3D) structure of the associated vasculature. Currently, computed tomography angiography (CTA) is the method-of-choice for preoperative vascular imaging in breast reconstruction surgeries. While CTA is capable of generating excellent anatomical details of perforator vessels, patients are also exposed to additional risks associated with the use of ionizing radiation and iodinated contrast agents. Magnetic resonance angiography (MRA) using intrinsic contrast mechanisms (without the use of any external contrast medium), such as velocity-encoded phase contrast, can generate accurate, high-resolution 3D vasculature maps without the risks associated with CTA. Therefore, non-contrast MRA is a more desirable alternative to CTA in preoperative planning of flap surgeries.

The overall objective of this pilot study is to develop and optimize preoperative MRA imaging protocols for various perforators commonly used in flap surgery with phantom and healthy volunteers, and to obtain clinical validation of the optimized protocols with a group of patients receiving flap surgery at the OSU Wexner Medical Center. Data obtained in this study may also serve as the basis for statistical planning of future clinical trials.

Based on our previous experience with other magnetic resonance imaging (MRI) techniques, we hypothesize that optimal MRA images can only be obtained with a carefully selected combination of imaging hardware, acquisition, and postprocessing factors. The main objective of this pilot study is to

determine this optimal combination through the comparison of image quality between different combinations.

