The secondary objective of this pilot study is to evaluate, both qualitatively and quantitatively (for details see below), the quality of the optimized MRA images and compare them with clinical CTA images. Our hypothesis is that the quality of the optimized MRA images is at least comparable to that of the CTA images. The quantitative measurements obtained from this pilot population will also serve as the preliminary data for future studies and be used in statistical calculations that determine their study population.

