## Preoperative Planning for Perforator Flaps

Because there is a large inter-patient variation in the number, size, and position of perforator vessels [Hallock 2001], careful, personalized preoperative planning for every patient is of essential importance to the success of perforator flap surgery. Initially, this was done with acoustic Doppler ultrasound sonography and color duplex sonography [Hallock 1994; Giunta 2000]. In this examination, a Doppler probe is scanned over the skin of the donor site. Pulsating Doppler signals mark out the presence of flow in blood vessels. The point with the loudest signal is identified as the position of the perforator. A major problem of the Doppler ultrasound technique is that its signal strength is only dependent on one component of the relative motion speed along the direction of the ultrasound beam. Therefore, a small vessel along the ultrasound beam direction may generate stronger signals than a large perforator running along an oblique direction. This technique thus tends to detect many small vessels that are not suitable for perforator flap surgery and yield a high proportion of false positive results. Giunta and colleagues reported that 47.6% of 271 “perforators” detected with acoustic Doppler ultrasound sonography were actually not dissected intraoperatively in DIEP and SGAP flap surgeries [Giunta 2000]. Yu et al. had similar findings for the ALT flap procedure, and observed that the accuracy of Doppler examination decreases with increasing body mass index [Yu 2006]. Other minor disadvantages of

Doppler ultrasound sonography include suboptimal presentation of images to the surgeons and the lack of the capability to reconstruct a 3D tomographic volume.

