Several other non-invasive imaging modalities, including near-infrared fluorescence angiography [Matsui 2010], CTA [Karunanity 2011; Rozen 2008a], and contrast enhanced MRA (CE-MRA) [Greenspun 2010; Neil-Dwyer 2009], have been evaluated in efforts of finding a better planning tool for perforator flap surgeries. Currently, the plastic surgery community considers CTA as the method-of-choice for preoperative planning in breast reconstruction surgeries using DIEP or SGAP/IGAP. Despite some recent critics on inaccuracy in perforator caliber measurement [Cina 2010], CTA has substantial advantages in several aspects compared with the traditional Doppler techniques: It generates less false positive results and is more sensitive than Doppler ultrasound in detecting perforators [Rozen 2008b]. It is also superior in visualizing the intramuscular course of the perforators and the superficial subcutaneous vascular network [Cina 2010]. CTA images can be rendered as a 3D volume for comprehensive preoperative planning, and saved for intraoperative display. This helps to substantially improve planning quality and reduce operative time. Acosta and colleagues reported that incorporating CTA into their workflow has led to a mean reduction of 90 minutes to the operative time of DIEP flap breast reconstruction [Acosta 2011].

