### **Data Analysis**

Standard postprocessing techniques including but not limited to noise filtering, co-registration to anatomical images, and 3D rendering will be applied to the optimal MRA images before the data are presented to the investigators for further analysis. The clinical CTA data will only be postprocessed with a 3D rendering algorithm because they already contain basic anatomical information.

De-identified optimal MRA and CTA data will be presented, in a randomized order, to the investigators for their independent assessment.

The radiologists will assess the imaging data on the following aspects:

- Imaging artifacts;
- Noise Level;

- Any other findings that may affect clinical interpretation of the images.

The plastic surgeons will assess the imaging data on the following aspects:

- The overall image quality;
- Anatomy accuracy;
- Vascular network continuity;
- Perforator branching pattern;
- Clinical applicability;
- Any other findings that may affect the planning, or the execution, or the follow up strategy of the flap procedure.

The plastic surgeons will also identify target perforators that are suitable to build a flap upon. An investigator will make the following quantitative measurements on each target perforator using a commercial workstation or custom-built software:

- Signal-to-noise ratio (SNR);
- Contrast-to-noise ratio (CNR) to muscle and fat;
- Perforator size;
- Length of the Perforator Intramuscular Course;
- Any other quantitative metrics that may support clinical decision-making.

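### Substitute CTAs are other people's scans chosen for clear perforators, while own CTAs are taken by recency, so the MRA–CTA comparison rests on two unequal comparators

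*Protocol*

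**What the plan says.** The Protocol's Clinical CTA Data Extraction section sets two rules for the comparator scan.

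- **Patient with an own pre-operative CTA, done or planned:** "an investigator will review their CTA cases available on OSUMC PACS and select the most recent one for further comparison and evaluation". No quality condition applies.
- **Patient without one and not expected to get one:** "a radiologist will review previously acquired CTA cases saved on OSUMC PACS that were obtained in the past 48 months", and is then to "select an age- and gender-matched case with clear depiction of the relevant perforator(s) for further comparison and evaluation". This is another person's scan, matched on age and gender only. The pool is not restricted to scans made for flap planning.

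Under Data Analysis, plastic surgeons rate both modalities on, among other things, "The overall image quality", vessel continuity and branching pattern. An investigator measures SNR, CNR, perforator size and intramuscular course length on each target perforator. The Statistical Analysis section plans a comparison of the MRA and CTA data sets and does not distinguish own from substitute CTAs. The comparison serves the secondary objective: "Our hypothesis is that the quality of the optimized MRA images is at least comparable to that of the CTA images".

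**The concern.** There are two separate problems.

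**Selection on quality.** A substitute enters because it shows the perforators clearly. That is not the same as the rated outcomes, but it is close to several of them. Own CTAs face no such condition, and neither do individual MRA images. If archived and own scans are otherwise of equal quality, the CTA side is raised in the substitute cases. This works against MRA. It is conservative for a hypothesis of comparability, but it distorts the estimated difference and lowers the chance of showing comparability that exists.

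**Person mixed with modality.** The OBJECTIVE section says that "there is considerable inter-patient variation in the number, size, and position of perforator vessels", and Preoperative Planning for Perforator Flaps repeats the point as the reason for planning each patient individually. Setting one person's perforator on MRA against another person's on CTA cannot show whether the two modalities agree on size or course length. Matching on age and gender does not fix either. This problem remains whatever the direction of the first.

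De-identified reading in random order limits reader bias. It cannot undo a selection made before reading, or supply a same-person scan.

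**Working it through.** The protocol states no margin, SD, test level or power for this comparison, so there is no figure of its own to reproduce. Everything below except n is an assumption.

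**Inputs**
- n = 50 evaluable patients (Design Overview).
- Ratings normal with SD 1, modalities truly equal, archive as good as own scans.
- Correlation r between MRA and CTA ratings: 0.3 or 0.6 in own pairs, 0 in substitute pairs.
- Correlation ρ between clarity and rating: 0.5; ρ = 1 is an upper limit.
- Share f of patients on substitutes; share q of archived scans that count as clear.
- One pooled paired t-test, two-sided 0.05. Comparability is shown if the lower 95% limit lies above −0.5 SD.

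**Mean shift.** If substitutes come from the clearest share q, their mean clarity rises by φ(z)/q, where z cuts off the top q and φ is the normal density. This gives 0.195 (q = 90%), 0.424 (75%) and 0.798 (50%). The shift of the MRA−CTA mean is −f·ρ·φ(z)/q:
- f = 40%, q = 75%: 0.4 × 0.5 × 0.424 = 0.085 SD against MRA (ρ = 1: 0.17)
- f = 40%, q = 50%: 0.4 × 0.5 × 0.798 = 0.16 SD against MRA (ρ = 1: 0.32)

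**Chance of wrongly declaring CTA better** (simulation, nominal 2.5%; ρ = 0.5 unless stated):

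| Substitutes | Clear | r = 0.3 | r = 0.6 |
|---|---|---|---|
| 10% | 90–95% | about 3% | about 3% |
| 20% | 90% | 3.2% | 3.2% |
| 20% | 75% | 4.2% | 4.5% |
| 40% | 90% | 4.1% | 4.2% |
| 40% | 75% | 6.4% | 7.3% |
| 40% | 50% | 13.6% | 15.7% |
| 40%, ρ = 1 | 75% | 15.4% | 18.5% |
| 40%, ρ = 1 | 50% | 42.7% | 53.6% |

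At ρ = 0.3 and 40% substitutes the figures are about 5% (75% clear) and 7–8% (50% clear). An unpaired test has the same mean shift, with 3–5% and 7–10% at ρ = 0.5.

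**Power to show comparability** (40% substitutes, ρ = 0.5; r = 0.3 / 0.6):
- no selection: 77% / 87%
- 90% clear: 71% / 81%
- 75% clear: 62% / 73%
- 50% clear: 46% / 56%

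**If the archive is poorer.** With 40% substitutes, 50% clear and ρ = 0.5, selection raises a substitute's mean rating by 0.5 × 0.798 = 0.40 SD. An archive 0.4 SD below own scans is therefore just offset, and the error returns to about 2.5% on each side. At 0.8 SD below, MRA is wrongly declared better in 13.5% / 16.1%.

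**Size and length.** With unit SD per modality, the SD of a difference is √(2(1−r)) within one person and √2 across unrelated persons, a ratio of √(1/(1−r)). For a within-person correlation of 0.8 or 0.9 this is 2.2 or 3.2. If matching leaves a correlation of 0.2 across persons, the ratio √(0.8/(1−r)) is still 2.0 or 2.8.

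**The case against.** - **Pooling is assumed.** The protocol asks only for suitable tests with correction for multiplicity, and an analysis plan not seen here could separate the two groups. True, and the error rates above apply only if they are pooled. But no analysis plan can undo how substitutes were chosen or provide a same-person CTA, and the selection rule is protocol content.
- **The large figures need heavy scenarios.** Also true. At 20% substitutes, or at 90% clear, the error is 3–4.5%, and the ρ = 1 rows are limits, not expectations. The share of substitutes may be low where, as the protocol says, "the plastic surgery community considers CTA as the method-of-choice for preoperative planning in breast reconstruction surgeries using DIEP or SGAP/IGAP". That statement does not cover TDAP or ALT flaps.
- **The net direction is uncertain.** A poorer archive can cancel the selection. In addition, MRA images receive noise filtering and co-registration while CTA receives only 3D rendering, which may favour MRA by an unknown amount. This weakens any claim about direction. It does not make the two rules equal.
- **The criterion has a purpose.** A perforator that cannot be seen cannot be measured, so some adequacy threshold is reasonable. Own CTAs pass no such threshold, however.
- **This is a pilot.** Protocol optimization and the MRA summary statistics for future sample sizes are unaffected. That limits the weight of the point; the secondary objective is still affected.

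**Conclusion.** The concern holds. The protocol fixes unequal rules for the CTA comparator, and for substitute cases it makes size and length comparisons that cannot show agreement between modalities. Both follow from the text without any calculation.

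The numerical impact is not known. It ranges from negligible (few substitutes, nearly all archived scans clear) to an error of 13–16% against a nominal 2.5%, with power down from 77–87% to 46–56%, at 40% substitutes and 50% clear with ρ = 0.5. These figures rest on pooling, on an archive as good as own scans, and on the assumed correlations and margin. The point should be fixed before comparator CTAs are selected and read, but it does not threaten the main objective.

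**What to change.** 1. State in the protocol that the main MRA–CTA comparison, and every comparison of perforator size and intramuscular length, uses only patients with their own CTA.
2. If substitutes are kept, report them separately, labelled, unpaired and descriptively, for image-quality measures only. Do not pool them with own-CTA pairs.
3. If the clear-depiction criterion is replaced, draw substitutes only from pre-operative CTAs acquired for flap planning at the same donor site, by a rule blind to image quality, for example the most recent age- and gender-matched scan. Record a scan on which the perforator cannot be measured as such, as for own CTAs. A quality-blind draw from any archived scan is not advised: if such scans average 0.8 SD lower (assumed) and are pooled at 40%, MRA would wrongly be declared better in 37–46% of studies.

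**Cost.** Wording only, with no extra scans or patients, but fewer pairs. The 95% half-width for a rating difference, t·√(2(1−r)/n), is, for r = 0.6 to 0.3:
- 50 pairs: 0.25–0.34 SD
- 30 pairs: 0.33–0.44 SD
- 20 pairs: 0.42–0.55 SD

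Thirty own pairs give 61% (r = 0.3) or 84% (r = 0.6) power at the assumed margin, against 62% or 73% for pooling at 75% clear. Where 90% are clear and r = 0.3, pooling has more power (71% against 61%). Own-CTA patients may also differ from the rest. The loss may be largest for TDAP and ALT flaps, where flap-planning CTAs for step 3 may be scarce too.

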### **Medical Record Review**

The medical record of all clinical patients will be reviewed by the investigators after the completion of their flap procedure to identify intra- and post-operative findings that may be correlated to pre-operative imaging data. Patient (age, obesity, radiation, chemotherapy, smoking, and other medical comorbidities) and surgical factors (flap type, laterality, and surgical time) that are known to affect free flap procedure outcomes will be collected.

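### Patients without their own CTA are paired with another person's CTA, which cannot give a within-patient MRA-CTA comparison of person-specific anatomy

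*Protocol*

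**What the plan says.** Clinical CTA Data Extraction sets two routes to the comparator scan. Where a patient has, or will have, a pre-operative CTA at the centre, "an investigator will review their CTA cases available on OSUMC PACS and select the most recent one for further comparison and evaluation". The other route begins "For patient subjects who do not have any pre-operative CTA on OSUMC PACS and are not expected to get one within the next 24 months". Here a radiologist searches archived CTAs from the past 48 months to "select an age- and gender-matched case" that shows the relevant perforators clearly, again for comparison and evaluation. Both routes end in the same use.

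Data Analysis applies one list of ratings and measurements to all MRA and CTA data. Surgeons rate, among other things, anatomy accuracy and branching pattern, and they pick target perforators. An investigator then measures each target perforator, including its size and the "Length of the Perforator Intramuscular Course". Statistical Analysis plans a comparison of the MRA and CTA data sets and does not distinguish the two sources of CTA.

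The Objective section states that "there is considerable inter-patient variation in the number, size, and position of perforator vessels", and Preoperative Planning for Perforator Flaps repeats this as the reason for planning each patient individually.

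**The concern.** Several of the compared items describe one person's vessels. In an own-CTA pair, both scans show the same anatomy, so a difference in measured size or course can be read as a difference between modalities. In a substitute pair the two scans have no vessel in common. Matching on age and gender does not fix the number, calibre or course of perforators, and the protocol's own account of variation between patients implies as much. The problem does not depend on how good the substitute scan is, since a perfect CTA of someone else still shows other vessels.

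At stake is the secondary objective, the comparison of optimized MRA with clinical CTA. If substitute pairs are analysed together with own-CTA pairs, person-to-person differences enter the result as if they were modality differences. Since the number of substitutes is neither stated nor capped, the affected share could be material.

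**Working it through.** The protocol gives no standard deviation, margin or power figure for this comparison, so there is no figure to reproduce. The main check is to set the sections side by side.

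1. Comparator source: own CTA or another person's CTA, both sent to the same evaluation (Clinical CTA Data Extraction).
2. Items: size, intramuscular course, branching, anatomy accuracy and target perforators, with no restriction by source (Data Analysis).
3. Analysis: the MRA and CTA data sets are compared without separating the sources (Statistical Analysis).
4. Premise: number, size and position vary widely between patients (Objective; Preoperative Planning for Perforator Flaps).

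From 1 to 4, modality and person are confounded in the substitute subset. Medical Record Review collects operative findings, but these could check only the patient's own MRA. They say nothing about the accuracy of someone else's CTA.

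**Illustration for perforator size (assumed SDs).** Let sb be the between-person SD and se the measurement SD of each modality.

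- Variance of the MRA-CTA difference, own CTA: 2·se².
- Variance with a substitute: 2·(se² + sb²), taking the two people as independent.
- Ratio: 1 + sb²/se².
- 95% limits: ±1.96 times the square root of the variance.

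Imaging Protocol Optimization gives typical diameters of 0.5 to over 1 mm. Reading 0.5 to 1.0 mm as ±2 SD gives sb = 0.5/4 = 0.125 mm. I take 0.20 mm as a higher value, and 0.03 to 0.10 mm for se.

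| sb (mm) | se (mm) | Own-CTA limits (mm) | Substitute limits (mm) | Variance ratio |
|---|---|---|---|---|
| 0.125 | 0.03 | ±0.08 | ±0.36 | 18.4 |
| 0.125 | 0.05 | ±0.14 | ±0.37 | 7.2 |
| 0.125 | 0.10 | ±0.28 | ±0.44 | 2.6 |
| 0.20 | 0.03 | ±0.08 | ±0.56 | 45.4 |
| 0.20 | 0.05 | ±0.14 | ±0.57 | 17.0 |
| 0.20 | 0.10 | ±0.28 | ±0.62 | 5.0 |

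A wider set (sb 0.2 to 0.4 mm, se 0.1 to 0.2 mm) gives ratios from 1 + 0.2²/0.2² = 2 to 1 + 0.4²/0.1² = 17. Those between-person SDs are high against the diameter range in the protocol.

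**If the two kinds of pair were pooled** (50 patients, sb = 0.125, se = 0.05, substitute share f): variance = (1 − f)·2·se² + f·2·(se² + sb²), and correlation = (1 − f)·sb²/(sb² + se²).

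| Substitute share | Patients | Correlation | Limits (mm) |
|---|---|---|---|
| 0% | 0 | 0.86 | ±0.14 |
| 10% | 5 | 0.78 | ±0.18 |
| 30% | 15 | 0.60 | ±0.23 |
| 50% | 25 | 0.43 | ±0.28 |
| 80% | 40 | 0.17 | ±0.34 |

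**Selection for clear depiction.** If, purely for illustration, clearly depicted vessels were the larger half of a normal distribution, substitutes would be larger on average by 0.798 × 0.125 = 0.100 mm. At a 30% share the pooled mean would shift by 0.3 × 0.100 = 0.030 mm towards CTA (standard error about 0.017 mm, not adjusted for the selection) with no modality difference at all.

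**The case against.** The strongest reply is that the protocol states no paired analysis. Its hypothesis concerns image quality, readers assess each set independently in random order, and the test is left open. A statistical analysis plan, which is not shown, might separate the two groups. This stands in part. Pooling and limits of agreement are illustrations here, not planned analyses. But the choice of comparator is data acquisition and is fixed in the protocol, and no later analysis can create a same-vessel comparison where none was imaged.

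Some stronger conclusions that a reader might draw are not supported:

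- **No comparison of any kind is possible.** An unpaired comparison of group means or depiction scores can be computed. It is confounded with person, and only within-patient agreement or accuracy is ruled out.
- **Pilot data for later trials are inflated.** Statistical Analysis takes those from the MRA measurements, which are the same whichever CTA is paired.
- **The match ignores donor site or must include body size.** Requiring the relevant perforators already ties the substitute to the donor site. Obesity is collected as a factor in flap outcome, and nothing in the protocol links it to CTA depiction, so matching on body size is a preference.

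It is also fair to say that the affected share may be small for some flaps, since the background calls CTA the method of choice for planning DIEP and gluteal breast reconstruction.

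**Conclusion.** The point holds for within-patient agreement or accuracy on perforator size, intramuscular course length, branching pattern, anatomy accuracy and target-perforator choice. In the substitute subset any MRA-CTA difference in these items mixes modality with person. That follows from the protocol's text alone.

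The size is uncertain. Across the assumptions tried, the variance of a size difference rises roughly 2 to 45 times, and substitute limits of ±0.36 to ±0.62 mm (sb 0.125 to 0.20 mm) are wide against vessels of about 0.5 to 1 mm. These figures rest on assumed SDs, on independence between the two people, and on the same vessel being measured on both scans of an own-CTA pair, which the protocol does not spell out. The overall effect also depends on the unstated share of substitutes. It bears on the secondary objective of a pilot study. Own-CTA pairs remain sound if analysed on their own, and the MRA summary statistics are untouched.

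**What to change.** In Clinical CTA Data Extraction, Data Analysis and Statistical Analysis:

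- Restrict the MRA-CTA comparison of size, intramuscular course, branching, anatomy accuracy and target perforators to patients with their own CTA.
- Use substitute CTAs only for image-quality items (artifacts, noise, overall quality, SNR, CNR), as a separate unpaired group that is not pooled with own-CTA pairs.
- Drop clear depiction as a condition for choosing a substitute, for example by taking the most recent eligible matched case. Otherwise report that group as favouring CTA, since no such condition applies to the MRA. Unpaired analysis alone does not remove this bias.
- State to which list vascular continuity and clinical applicability belong, and report how many patients have each kind of CTA.

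This is a change of wording and needs no new scan or visit. The cost is fewer patients in the anatomical comparison, though those removed carry no within-patient information on these items.
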